**Table 5: Ruxolitinib dose adjustment**

CTCAE grade 3 or greater bleeding related to low platelets	Non-transfused platelets		
	<10 $\times 10^9$ /L	10-50 $\times 10^9$ /L	>50 $\times 10^9$ /L
Hold. Reassess 2 weeks after resolution of bleeding	Hold	5 mg daily	5 mg twice daily 

For cycles 2, 3, and 4, if platelets improve to  $>100 \times 10^9$ /L, a dose increase to 10 mg twice daily may be considered.

### 8.5 Re-screening Eligibility for Cycles 2- 4

Patients will be screened for eligibility to continue onto each subsequent cycle of therapy. Patients with disease progression, new GVHD (except grade I acute GVHD), prolongation of the most recent cycle to more than 8 weeks (for any reason), or inadequate cell dose for further DLI will not receive further treatment on study. Rescreening will be an ongoing process. When patients meet the eligibility criteria outlined below, they may begin subsequent cycles.

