### 9.3 Risks Due to DLI

#### Acute Infusion Reaction Following Donor Lymphocytes

Although infusion of donor lymphocytes has reportedly not been associated with serious acute hypersensitivity reactions, patients will be closely watched for the occurrence of hypotension, dyspnea and angiodema during the infusion and immediately thereafter. Corticosteroids should be avoided and acetaminophen and Benadryl may be administered as needed.

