## **12.2 AE Documentation**

AE reporting will occur via data entry into the study eCRF. AEs reported through expedited processes (e.g., reported to Incyte, IRB, FDA, etc.) must also be reported in routine study data submissions. Patients will be monitored for adverse events after the subject has signed the ICF through 30 days after the last dose of study drug. Adverse events recorded in the eCRFs include the following:

- CTCAE grade 3 and greater allergic reactions related to ruxolitinib or decitabine occurring until 30 days after the last treatment on study
- CTCAE grades 3 and greater organ toxicity (cardiac, dermatologic, gastrointestinal, hepatic, pulmonary, renal/genitourinary, or neurologic) occurring until 30 days after the last treatment on study
- aGVHD III-IV occurring until 3 months after the last cycle of treatment
- CTCAE grade 4 neutropenia lasting more than 14 days, occurring until 30 days after the last treatment on study
- CTCAE grades 3 and greater febrile neutropenia, or grade  $\geq 3$  neutropenia with documented infection, occurring until 30 days after the last treatment on study
- CTCAE grade 4 thrombocytopenia lasting more than 14 days if pre-treatment platelet count  $> 100 \times 10^9/L$ , occurring until 30 days after the last treatment on study

In addition any event meeting the definition of a serious adverse event (SAE) regardless of attribution that occurs during this period will be documented in the source document and recorded in OnCore.

After the final treatment visit, monitoring for adverse event will become less frequent based on the schedule in [Section 11](#) and only events at least possibly related to study treatment (based on the table above) will be documented upon knowledge.

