### **14.3 Correlative Endpoints**

- Incidence and severity of adverse events (AEs) and serious AEs (SAEs) until 3 months after day 1 of the last received cycle
- Correlative studies: T cell and NK cell subset analysis by flow cytometry, correlation between TP53 mutation and response, clonal dynamics during and after the course of therapy

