### **Secondary and exploratory analysis**

Analysis of secondary endpoints will be primarily descriptive. Progression-free survival will be estimated by Kaplan-Meier curves. Cumulative Incidence will be used to estimate the probability of relapse and acute GVHD, treating non-event death as a competing risk. Likewise, relapse will be treated as a competing risk when estimating the probability of non-relapse mortality. Response and the number of patient in complete remission will be estimated with simple proportions. Summary statistics using frequencies and proportions of patients will be used to assess adverse and severe adverse events and medians, ranges and descriptive plots for immune therapy. The correlation between *TP53* mutation and response will be assessed with a chi-square test or Fisher's exact test depending on expected cell frequencies. Similar statistics will be used for the correlation against clonal dynamics curing and after the course of therapy.

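### Section 12.2 does not require recording of some non-serious grade 3–4 events (prolonged low platelets from a low baseline, DLI allergic reactions, some bleeding and infection), so non-serious AE incidence may be understated

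*Combined protocol and SAP*

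**What the plan says.** Section 12.2 gives six types of event for the eCRF. Four bear on this point:

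- **Platelets:** "CTCAE grade 4 thrombocytopenia lasting more than 14 days if pre-treatment platelet count" was above 100 × 10⁹/L. The neutropenia item beside it carries no baseline condition: "CTCAE grade 4 neutropenia lasting more than 14 days, occurring until 30 days after the last treatment on study".
- **Allergic reactions:** "CTCAE grade 3 and greater allergic reactions related to ruxolitinib or decitabine". DLI is not named, although the note at the start of Section 12 defines study drug as all three components.
- **Infection:** listed only as febrile neutropenia, or as neutropenia of grade 3 or more with a documented infection.
- **Organ toxicity:** grade 3 or more in seven systems (heart, skin, gut, liver, lung, kidney/urinary tract, nervous system), not tied to any one drug.

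The other two items are severe acute GVHD and the neutropenia item quoted above. Section 12.2 also has every SAE recorded, whatever its attribution. Section 12.1 counts hospital admission, prolonged admission and important medical events as serious.

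Incidence and severity of AEs and SAEs is a correlative objective and endpoint (Sections 1.3 and 14.3). Section 15.2 gives the analysis: "Summary statistics using frequencies and proportions of patients will be used to assess adverse and severe adverse events".

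**The concern.** The plan itself treats the unlisted events as relevant.

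- Section 9 lists low platelets as very common with both ruxolitinib and decitabine. Section 9.3 reports marrow aplasia in 10–15% of DLI cases.
- "CTCAE grade 3 or greater bleeding related to low platelets" is a ruxolitinib dose-adjustment event in Table 5, yet 12.2 has no bleeding item.
- Section 8.3 requires monitoring during the infusion. Section 9.3 says that "patients will be closely watched for the occurrence of hypotension, dyspnea and angiodema during the infusion and immediately thereafter".
- Section 9.1 lists CMV infection and sepsis among the expected events with ruxolitinib in GVHD.

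A site that follows 12.2 as written need not record a patient whose platelets fall from 90 to grade 4 for several weeks and who is managed without an admission. The proportions reported under Section 15.2 will describe the safety of a new three-part regimen. If such events are left out, the non-serious part of that description will look better than it should, and readers will not be able to tell by how much.

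**Working it through.** The plan states no expected AE rate, so there is no figure to reproduce. The check is to follow each kind of event through 12.2, and then to do one piece of arithmetic on the platelet condition.

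**Step 1. Which events have a route into the eCRF?**

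| Event | Own list item? | Organ-toxicity item? | SAE rule? | Left unrecorded |
|---|---|---|---|---|
| Grade 4 thrombocytopenia >14 days, baseline >100 | Yes | – | If serious | None |
| Same, baseline ≤100 | No | No | If serious | Non-serious events |
| Grade ≥3 DLI reaction | No | In part (skin, respiratory) | If serious | Non-serious reactions outside the seven systems, e.g. some hypotension |
| Grade ≥3 bleeding | No | In part (gut, lung, urinary tract, nervous system) | If serious | Non-serious bleeds elsewhere |
| Grade ≥3 infection without neutropenia | No | Not clearly | If serious | Non-serious infections |
| Acute GVHD III–IV | Yes | – | If serious | None |
| Prolonged or febrile neutropenia | Yes | – | If serious | None |

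Each gap in the last column is confined to non-serious events.

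**Step 2. Arithmetic of the platelet condition.**

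Inputs:

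- N = 32 evaluable patients (Section 15.1). With 5% not evaluable, 32 / 0.95 = 33.7, rounded up to 34, which agrees with the planned enrolment.
- f = share of patients with pre-treatment platelets above 100 × 10⁹/L. The documents do not give it, and Section 5.1 sets no platelet minimum. Assumed range: 10% to 75%.
- r = true rate of prolonged grade 4 thrombocytopenia, assumed equal in both baseline groups. Illustrative values: 50% and 30%.

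Patients counted by the list item = N × f × r. As a proportion of all patients this is f × r. Since r cannot exceed 1, the proportion cannot exceed f.

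| f | Counted, r = 50% (true 16) | Reported over 32 | Counted, r = 30% (true 9.6) | Reported over 32 |
|---|---|---|---|---|
| 10% | 1.6 | 5% | 1.0 | 3% |
| 25% | 4 | 12.5% | 2.4 | 7.5% |
| 50% | 8 | 25% | 4.8 | 15% |
| 75% | 12 | 37.5% | 7.2 | 22.5% |

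With equal rates, the list item recovers the fraction f of the true events. If the rates differ by baseline group, that fraction changes, but the ceiling f on the reported proportion stays. These are lower limits of capture, because thrombocytopenia that qualifies as an SAE is added back. They also assume that all patients form the denominator, which Section 15.2 does not say for an item with a baseline condition.

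**The case against.** The strongest reply is that 12.2 has two safety nets. Every SAE is recorded whatever its cause, so sepsis, a bleed needing admission or a serious DLI reaction will be captured, and SAEs are part of the endpoint. The organ-toxicity item takes in many bleeds and several of the DLI reactions that Sections 8.3 and 9.3 name. Both points stand and limit the gap to non-serious events. They do not close it: prolonged low platelets managed with outpatient transfusion are not automatically serious, and whether they count as an important medical event is a judgement that may differ by site.

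A second reply is that the list is introduced by the word *include* and so may be open. That does not settle the matter. If the list is open, sites may record different events and the proportions are hard to interpret; if it is closed, the events are missed.

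A third is that a baseline condition has a sound reason: in relapsed marrow disease, low starting platelets make attribution to treatment difficult. This is fair. Reporting by baseline group keeps that distinction without discarding the data.

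A reader might also infer more than the documents support:

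- **That many patients are expected to start at or below 100.** Sections 8.1 and 8.4 do speak of platelets recovering or improving beyond 100, but for cycles 2 to 4. That can describe recovery from cycle 1 treatment just as well as a low baseline.
- **That DLI reactions and bleeds would be reported as zero.** The organ-toxicity item and the SAE rule rule this out.
- **That serious DLI hypersensitivity is a known frequent problem.** Section 9.3 says that serious acute hypersensitivity has reportedly not been seen.

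**Conclusion.** The point holds in a limited form. Section 12.2 does not require recording of four kinds of non-serious event: prolonged grade 4 thrombocytopenia in patients who start at or below 100 × 10⁹/L; grade 3 or higher allergic reactions to DLI that fall outside the organ-toxicity item; grade 3 or higher bleeding outside the seven organ systems; and grade 3 or higher infection without neutropenia. Non-serious AE incidence may therefore be understated.

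The size cannot be derived, because neither the baseline platelet distribution nor the share of these events that would be serious is given. The figures above (for example 12.5% in place of 50% when a quarter of patients start above 100) are illustrations that rest on an assumed f, equal rates in both groups, an all-patient denominator and no SAE capture.

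It would be wrong to conclude that the regimen's main toxicities go unrecorded. Section 2.1 calls severe GVHD the major toxicity of DLI. Grade III–IV is listed in 12.2 and drives the stopping rule in 15.4, and grade II–IV is a secondary endpoint. Prolonged and febrile neutropenia are listed too. Nor does the ceiling f apply to everything reported on platelets; it applies to one list item before SAEs are added. The endpoint is correlative and descriptive, and no test or stopping rule depends on the gaps. This is a worthwhile and inexpensive improvement, not a threat to the trial's main conclusions.

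**What to change.** Amend Section 12.2 as follows:

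1. Record prolonged grade 4 thrombocytopenia in all patients, together with the pre-treatment count. In Section 15.2, report it separately for baseline >100 and ≤100 × 10⁹/L, each with its own denominator.
2. Word the allergic-reaction item to cover ruxolitinib, decitabine or DLI, in line with the definition of study drug in Section 12.
3. Add an item for bleeding of grade 3 or higher.
4. Add an item for infection of grade 3 or higher, irrespective of neutrophil count.

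The blood counts and AE assessments are already in the Section 11.1 calendar, and no treatment rule changes. The cost is a few more eCRF entries per patient, and reported AE rates that will be higher than under the present list.

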## 12.3 SAE Documentation and MCC Reporting Requirements

Individual institution reporting requirements are listed in [section 12.5](#).

All SAEs are documented using the MCC OnCore SAE Report Form and reported within the timeframes indicated below:

Agency	Criteria for reporting	Timeframe	Form to Use	Submission address/ fax numbers
U of MN IRB	Events requiring prompt reporting including, but not limited to unanticipated death of a locally enrolled subject(s); new or increased risk; any adverse event that require a change to the protocol or consent form or any protocol deviation that resulting in harm. For a complete list refer to http://www.research.umn.edu/irb/guidance/ae.htm l#.VC7xral0-sh	Within 5 business days of event discovery	MCC SAE Report Form	ETHOS copy SAEs to Incyte at [contact] (note: Incyte does not need copies of deviations)
	Deviations from the protocol, per current IRB reporting requirements		Deviation Report	
FDA	Unexpected and fatal or unexpected and life threatening suspected adverse reaction	no later than 7 Calendar Days	MCC SAE Report Form	Submit to FDA as an amendment to IND
	1) Serious and unexpected suspected adverse reaction or 2) increased occurrence of serious suspected adverse reactions over that listed in the protocol or investigator brochure or 3) findings from other sources (other studies, animal or in vitro testing)	no later than 15 Calendar Days		
	Events that trigger an early study stopping rule.	no later than 7 Calendar Days	Event Form	
Incyte Corporation	Every SAE, regardless of suspected causality (eg, relationship to study drug(s) or study procedure or disease progression), occurring after the subject has signed the ICF through the last study visit (or 30 days) after the last dose of study drug, whichever is later) must be reported to the Incyte within 24 hours of learning of its occurrence, Incyte may request follow-up and other additional information from the Sponsor Investigator.	Within 24 hours of event discovery	MCC SAE Report Form	[contact]
Masonic Cancer Center SAE Coordinator	Events that count toward early study stopping rule.	At time of reporting	Event Form	SAE Coordinator [contact] with copy to Incyte

**Expedited SAE Reporting Requirements:**

Report Within 24 Hours: SAEs must be reported expeditiously to the Masonic Cancer Center Affiliate Sites Manager within 24 hours of knowledge.

**12.4 Early Stopping Rule Events Documentation and Reporting Requirements**

The following events count toward an early study stopping rule per [Section 15.4](#) and must be reported to the MCC Affiliate Sites Manager and to Incyte Pharmaceuticals using the Event Form found OnCore under the reports tab: grade III-IV aGVHD until 3 months after the last cycle of treatment.

An event that counts toward an early stopping rule does not necessarily constitute a SAE and should be reported as such only if they meet the criteria for reporting as defined in [Section 12.3](#).

**12.5 Institutional Event Reporting Table**

Individual institutional sites will be responsible for reporting any event meeting local reporting requirements to their institutional IRB and/or other research oversight committees.

Institutional sites will be responsible for reporting events as defined in [sections 12.1, 12.2, 12.3](#) and [12.4](#) within the following time frames to the MCC Affiliate Sites Manager

Event Type	Reporting Timeframe	OnCore Form to Use	Report to**
Any event meeting the definition of a SAE occurring after the subject has signed the ICF through the last study visit (or 30 days after the last dose of study drug, whichever is later)	Within 24 hours of knowledge	SAE Report Form	Masonic Cancer Center (MCC) Affiliate Sites Manager [contact] The affiliate manager will submit SAEs to Incyte ([contact] )
Stopping Rule Events as defined in section 12.4	Within 24 hours of knowledge	Stopping Rule Event Form	Local institutional IRB or other entities per institutional policies and guidelines
Major and Critical Clinical Deviations, as defined in Section 12.1 .	Within 5 working days of knowledge	Deviation Report Form	

Event Type	Reporting Timeframe	OnCore Form to Use	Report to**
Minor Deviations, as defined in Section 12.1 .	Per Institutional Policy	n/a (record in Deviations Tab) but it is not necessary to report the event to MCC	For UMN MCC only: minor deviations are reported to the UMN IRB by the study's regulatory specialist per IRB reporting requirements.  For Affiliate Sites: minor deviations are not reportable to the Masonic Cancer Center. Report to local institutional IRB or other entities per institutional policies and guidelines.

\*\*events occurring at the University of Minnesota are reported to the study's Regulatory Specialist who will submit Incyte and other entities as usual

## 13 Study Data Collection and Monitoring

### 13.1 Data Management

This study will collect regulatory and clinical data using University of Minnesota CTSI's instance of OnCore® (Online Enterprise Research Management Environment).

The Oncore database resides on dedicated secure and PHI compliant hardware consisting of 3 physical servers: dev, DR, and production. The dev server is located in the University of Minnesota (UMN) datacenter (WBOB) and houses six database instances (test, train, sandbox, mcc reports, oncdm, and vendor) that are backed up locally because the data is refreshed from Oncore production data. The production server is located in the UMN datacenter (WBOB). All the data servers are managed by the Academic Health Center – Information Systems (AHC-IS) virtual servers which utilize clustered infrastructure to provide real-time failover of virtual servers. This real-time clustering is physically limited to the UMN data center. All relevant AHC IS procedures related for PHI compliant servers (as required by the Center of Excellence for HIPAA Data) apply to Oncore databases.

The integrated data will be stored in PHI compliant servers managed by AHC IS with access given to those authorized users in the Clinical and Translation Science Institute Informatics team (CTSI BPIC and MCC CISS). The data will be integrated and extracted to researchers through the CTSI Informatics team and will be delivered through secure and compliant mechanisms (e.g. AHC IE data shelter, BOX, sftp, etc). If data de-identification is needed, then compliant AHC IE data de-identification tools will be used. The informatics team will grant the IRB approved study team members access to data.

Additional data about correlative laboratory samples generated by the Masonic Cancer Center Translational Therapy Laboratory (TTL) from the protocol-directed correlative research samples is stored in their Laboratory Information Management System (LIMS). The LIMS database application is also stored on a production server located in the UMN datacenter (WBOB) and is managed by the Academic Health Center

Key study personnel are trained on the use of OnCore and will comply with protocol specific instructions embedded within the OnCore.

### **13.2 Case Report Forms**

Participant data will be collected using protocol specific electronic case report forms (e-CRFs) developed within OnCore based on its library of standardized forms. The e-CRF will be approved by the study's Principal Investigator and the Biostatistician prior to release for use. The Study Coordinator or designee will be responsible for registering the patient into OnCore at time of study entry, completing e-CRFs based on the patient specific calendar, and updating the patient record until patient death or end of required study participation.

### **13.3 Data and Safety Monitoring Plan (DSMP)**

The study's Data and Safety Monitoring Plan will be in compliance with the University of Minnesota Masonic Cancer Center's Data & Safety Monitoring Plan (DSMP), which can be accessed at <https://z.umn.edu/dsmp>.

For the purposes of data and safety monitoring, this study is classified as high risk. Therefore the following requirements will be fulfilled:

- At least bi-annual review of the study's progress by the Masonic Cancer Center Data and Safety Monitoring Council (DSMC).
- The PI will comply with at least twice yearly monitoring of the project by the institution's monitoring services.
- The PI will oversee the submission of all reportable adverse events per [Section 12.3](#) to the Masonic Cancer Center's SAE Coordinator, the University of Minnesota IRB, and the FDA.
- The PI with the CTO has oversight responsibility for trial monitoring at affiliate sites.

In addition, at the time of the continuing review with the University of Minnesota IRB, a copy of the report with any attachments will be submitted to the Cancer Protocol Review Committee (CPRC).

### **IND Annual Reports**

In accordance with regulation 21 CFR § 312.33, the Sponsor-Investigator will submit a progress report annually. The report will be submitted within 60 days of the anniversary date that the IND went into effect.

### **13.4 Teleconferences – Lead Site and Affiliate Site**

Regular teleconferences to facilitate communication between participating sites regarding the study's progress, patient updates, summary of safety reports, case report form completion, and other issues for discussion. The University of Minnesota Affiliate Manager will be responsible for arranging these teleconferences and preparing the agenda. Meetings will occur at least every 3 weeks; however, these may be scheduled more or less frequently at the discretion of the lead institution. Participation of a minimum of one representative from each affiliate site will be required. These teleconferences are in addition to other previously described site interactions including centralized patient registration, institutional and MCC required reporting of safety related issues, case report form completion in the study's central database (OnCore) and affiliate oversight through self-monitoring in compliance with the Masonic Cancer Center's Data and Safety Monitoring plan.

### **13.5 Affiliate Site Monitoring**

The PI ([name]) with the CTO has oversight responsibility for trial monitoring at affiliate sites. Affiliate sites must self-monitor following the University of Minnesota Masonic Cancer Center Data and Safety Monitoring Plan (DSMP - <http://z.umn.edu/dmsp>).

The investigator will permit study-related monitoring, audits, and inspections by the study's Principal Investigator or any designees, the local IRB, government regulatory bodies, and University of Minnesota compliance groups. The investigator will make available all study related documents (e.g. source documents, regulatory documents, data collection instruments, study data, etc.). The investigator will ensure the capability for inspections of applicable study-related facilities (e.g. pharmacy, diagnostic laboratory, etc.) will be available for trial related monitoring, audits, or regulatory inspections.

